## 10. STATISTICAL PLAN

This section provides the basis for the SAP for the study. The SAP may be revised during the study to accommodate amendments to the clinical study protocol and to make changes to adapt to unexpected issues in study execution and data that may affect the planned analyses. The final SAP will be issued before the database is locked after the double-blind period completion.

Analysis variables are listed in Section [4](#).

## 10.1. Statistical Hypothesis

Let  $\mu_0$  and  $\mu_1$  be the population means of the percent change from baseline in LDL-C at week 12 under placebo and alirocumab, respectively for the primary analysis. For the primary and main efficacy variables, the following null hypothesis and alternative will be tested:

$$H_0 : \mu_0 = \mu_1 \text{ versus } H_1 : \mu_0 \neq \mu_1$$

## 10.2. Justification of Sample Size

Patients will be randomized in the double-blind treatment period to alirocumab or placebo in a ratio of 2:1 respectively, with the primary efficacy hypothesis comparing the alirocumab-treated group to the placebo group at week 12. For the primary efficacy hypothesis during the double-blind treatment period, an initial total sample size of 51 patients (34 patients in the alirocumab-treated group and 17 patients in the placebo group) will have 90% power to detect a difference in mean percent change in LDL-C of 20%, with a two-sided significance level and assuming a standard deviation (SD) of 20%. Taking into account a 5% non-evaluable patient rate for the primary efficacy endpoint, the initial study sample size is increased to 54 patients (36 patients in the alirocumab-treated group and 18 patients in the placebo group).

Following the Blinded Sample Size Adjustment process (see below for details), the total study sample size will increase to approximately 74 patients, adding approximately 20 patients to the initial study sample size.

### Blinded Sample Size Adjustment

Referencing the ICH E9 regulatory guidance, the study sample size may be re-estimated after approximately 75% of the patients reach the week 12 visit in the double-blind treatment period to ensure adequate power in case of a larger-than-expected variability in the data. The sample size re-estimation will be based on the actual blinded pooled standard deviation (adjusted as described in [Kieser 2003](#)) for the primary efficacy measure. Since the patients' post-baseline LDL-C levels are masked to all study participants (patients, site personnel, and sponsor staff), the blinded pooled standard deviation will be calculated by a designated unblinded CRO statistician who will have access to the lipid data. As mentioned in Kieser and Friede ([Kieser 2003](#)), the blinded sample size re-estimation does not affect type I error materially for continuous endpoints.

This re-estimation procedure will assess the need for an increase in sample size and will maintain the initial planned enrollment if the procedure yields a smaller sample size (restricted recalculation). The result of this procedure is non-binding, since the decision to increase the sample size will also take into account other study execution factors (eg, availability of patients). In the case the re-estimated sample size is implemented, a protocol amendment will document the modification.

The blinded sample size adjustment process was implemented in October 2018 when approximately 75% of the patients reached the week 12 visit. The Kieser adjusted pooled standard deviation for LDL-C percent change from baseline was calculated at Week 12 to be 35%, which is larger than the protocol initial planned standard deviation of 20%. Applying the Kieser adjusted pooled standard deviation of 35 (while keeping all other assumptions as described in the protocol), the sample size would increase to 156 patients. With this large sample size increase, enrollment of

additional patients with HoFH, a rare disease, depends on the operational feasibility to identify eligible patients. After an assessment to identify eligible patients, a total sample size of 156 patients is not operationally feasible, but an additional 20 patients is considered realistic. Maintaining all other initial sample size assumptions, a new sample size of approximately 74 patients yields 61% power to detect a treatment group difference in mean percent change in LDL-C of 20%. Taking into account the conservative nature of the assumptions for the initial protocol sample size calculation, the new study sample size of approximately 74 patients will be implemented.

### 10.3. Analysis Sets

#### 10.3.1. Efficacy Analysis Sets

##### Intent-to-Treat Primary Efficacy Analysis Set:

The primary efficacy analysis population is the ITT population (also known as the full analysis set), defined as all randomized patients who had at least 1 measurement value for LDL-C before the first dose of double blind investigational study drug (ie, baseline).

Patients in the ITT population will be analyzed according to the treatment group allocated by randomization (i.e., as-randomized treatment group).

##### Modified Intent-to-Treat Analysis Set:

The modified (m)ITT population is defined as the all randomized population who took at least 1 dose or part of a dose of double-blind investigational study drug and has an evaluable primary endpoint. The endpoint is considered as evaluable when both of the following conditions are met:

- Availability of at least 1 measurement value for LDL-C before first dose of double-blind investigational study drug (ie, baseline).
- Availability of at least 1 LDL-C value during the efficacy treatment period and within one of the analysis windows in the double-blind period up to week 12. The efficacy treatment period is defined as the time from the first double-blind investigational study drug injection up to 21 days after the last double-blind investigational study drug injection, or the first dose of the open-label investigational study drug, whichever is earlier.

Patients in the mITT population will be analyzed according to the treatment group allocated by randomization.

#### 10.3.2. Safety Analysis Set

The safety analysis set (SAF) includes all randomized patients who received any double-blind investigational study drug; it is based on the treatment received (as treated). Treatment compliance/administration and all clinical safety variables will be analyzed using the SAF.

#### 10.3.3. The Open-Label Analysis Set

For the open-label treatment period, the open-label extension population for all measurements (efficacy, safety, PK and ADA) will be defined as those patients who received at least 1 dose or part of a dose of open-label investigational study drug alirocumab.

#### 10.3.4. Other Analysis Sets

For the double-blind treatment period, the PK and the ADA analyses will be performed on all randomized patients who received any double-blind investigational study drug, and further:

- The PK population will also require at least 1 non-missing result after the first dose of double-blind investigational study drug.
- The anti-alirocumab antibody analysis will be performed on all treated patients (safety population) with a blood sample at week 0 (baseline) and at least 1 evaluable blood sample for anti-alirocumab antibodies after the first dose of study drug.

### 10.4. Statistical Methods

For continuous variables, descriptive statistics will include the following information: the number of patients reflected in the calculation (n), mean, median, SD, minimum, and maximum.

For categorical or ordinal data, frequencies and percentages will be displayed for each category.

#### 10.4.1. Patients Disposition

Screened patients are defined as any patient who signed the ICF (informed assent form).

Randomized patients consist of all screened patients with a double-blind treatment kit number allocated and recorded in the IVRS/IWRS database, regardless of whether the treatment kit was used or not. Patients treated in the double-blind treatment period without being randomized, or treated with a double-blind treatment kit before the randomization will not be considered as randomized and will not be included in any analysis population. The safety experience of patients treated and not randomized will be reported separately.

For any patient randomized more than once during the double-blind treatment period, safety data from the first randomization will be included in the double-blind safety population, with the safety data associated with the later randomization reported separately. Since this is expected to be a rare event, inclusion of efficacy data from the patient randomized more than once in the efficacy population will be decided on a case-by-case basis prior to the unblinding of treatment assignments, and will be documented in the clinical study report.

Lastly, patients in the open-label treatment period consist of all double-blind treated patients who receive any amount of open-label alirocumab treatment.

#### 10.4.2. Demography and Baseline Characteristics

Demographic and baseline characteristics will be summarized descriptively by treatment group on the randomized population for the double-blind treatment period and again on the open-label population for the open-label treatment period (which will also include the patient total). Continuous variables will be summarized with mean, median, SD, minimum, and maximum. Categorical variables will be summarized with frequency and percentage.

### 10.4.3. Efficacy Analyses

#### 10.4.3.1. Primary Efficacy Analysis

For the double-blind primary comparison of the alirocumab treated group to the placebo treated group, the percent change from baseline in LDL-C at week 12, as defined in Section 4.2.1 will be analyzed in the ITT population using a mixed-effect model with repeated measures (MMRM) approach. All post-baseline data available within week 4 to week 12 analysis windows will be used and missing data are accounted for by the MMRM model. The model will include the fixed categorical effects of treatment group (alirocumab versus placebo), randomization strata (undergoing apheresis treatment [Yes vs. No] per IVRS/IWRS), time point (weeks 4, 8, 10, 12), and treatment-by-time point interaction, strata-by-time point interaction, as well as the continuous fixed covariates of baseline LDL-C value and baseline value-by-time point interaction. Model assumptions for normality will be explored prior to the analysis testing.

This model will be run using Statistical Analysis Software (SAS) mixed procedure with an unstructured correlation matrix to model the within-patient errors. Parameters will be estimated using restricted maximum likelihood method with the Newton-Raphson algorithm. Denominator degrees of freedom will be estimated using Satterthwaite's approximation. This model will provide baseline adjusted least-squares means estimates at week 12 for both treatment groups with their corresponding standard errors.

Let  $\mu_0$  and  $\mu_1$  be the population means of the percent change from baseline in LDL-C at week 12 under placebo and alirocumab, respectively. The hypothesis that will be tested is " $H_0: \mu_0 = \mu_1$ " versus " $H_1: \mu_0 \neq \mu_1$ ". Therefore, the alirocumab treated group will be compared to the placebo group using an appropriate contrast statement tested at the 2-sided 0.05 level, with corresponding least squares estimate of mean difference, SE and 95% confidence interval.

Robustness of this statistical method will be assessed via sensitivity analyses detailed in the SAP, including a different methodology to assess the potential violation of the missing-at-random assumption, specifically a pattern mixture model (PMM). For the PMM, the imputation model will account for the differing missing value patterns based on LDL-C collected in the presence or absence of study treatment administration for those patients randomized into the study.

#### 10.4.3.2. Secondary Efficacy Analysis

The key secondary efficacy endpoints (defined in Section 4.2.2.1) and other secondary efficacy endpoints (described in Section 4.2.2.2 for the double-blind treatment period, descriptive summaries and analyses will be performed in the ITT population or mITT population, corresponding to the specified estimand for the endpoint.

For descriptive summaries, percent change, and when appropriate, absolute change from baseline in LDL-C, total-C, HDL-C, TG, and non-HDL-C will be provided at each time point for each treatment group. All measurements, scheduled or unscheduled, will be assigned to analysis windows defined in the SAP in order to provide an assessment for these time points. Laboratory assessments other than the ones provided by the central laboratory will be excluded. For TG, measurements on not fasting patients will be excluded. The time profile of each parameter will be plotted by treatment group with the corresponding standard errors. Similar tables (with either

percent change from baseline or absolute change from baseline for the ratio) and plots will be provided for other efficacy parameters: ApoB, ApoA-1, ratio ApoB/ApoA-1, Lp(a).

Multiple types of measurements are planned to be analyzed during differing time points in the trial, specifically continuous measurements expected to have a normal distribution (example: percent change in LDL-C), continuous measurements expected to have a non-normal distribution (example: TG), and binary measurements (example: proportion of patients with at least 30% reduction in LDL-C).

#### I. Continuous endpoints anticipated to have a normal distribution

Continuous secondary variables defined in Section 4.2.2 anticipated to have a normal distribution (ie, lipids other than TG and Lp(a)) will be analyzed in the analysis populations using the same MMRM model as for the primary endpoint. Specifically, the model will contain fixed categorical effects of treatment group, randomization strata, planned time points up to week 12, strata-by-time point interaction and treatment-by-time point interaction, as well as the continuous fixed covariates of corresponding baseline value and baseline value-by-time point interaction.

#### II. Continuous endpoints anticipated to have a non-normal distribution

Continuous secondary efficacy endpoints defined in Section 4.2.2, anticipated to have a non-normal distribution (ie, TG and Lp(a)), will be analyzed in the analysis populations using a robust regression model (ie, ROBUSTREG SAS procedure with M-estimation option) with treatment group and randomization strata as main effect and corresponding baseline value(s) as covariate. Missing values will be addressed using a multiple imputation approach, which will be described in the SAP. The variables in the multiple imputation model will at least include the same variables as used in the robust regression model. The treatment group combined means will be provided with respective SE estimates. The combined mean difference between the treatment groups will be provided with the SE, 95% confidence interval and p-value.

#### III. Binary endpoints

Binary secondary efficacy endpoints defined in Section 4.2.2 will be analyzed in the analysis populations using stratified logistic regression (using the strata option of the SAS logistic procedure) with treatment group as main effect and corresponding baseline value(s) as covariate, stratified by randomization factor (as per IVRS). Missing values will be addressed using a multiple imputation approach which will be described in the SAP. The variables in the multiple imputation model will at least include the same variables as used in the logistic regression model. Treatment effects will be compared and the combined odds ratio estimate between the treatment groups, with their corresponding 95% CIs and p-value will be provided. In the data dependent case that the logistic regression method is not applicable (eg, the response rate is zero in 1 treatment arm and thus the maximum likelihood estimate may not exist), the last observation carried forward approach would be used for handling of missing values and an exact conditional logistic regression would be performed to compare treatment effects. The last observation carried forward imputation method will consist of using the last value obtained up to the week 12 time window to impute the missing week 12 value.

#### 10.4.3.3. Other Efficacy Endpoints

During the open-label treatment period, efficacy variables will be explored through descriptive statistics at each scheduled visit for the total patients administered open-label study treatment (total), as well as by the patient subgroups of study treatment received in the double-blind treatment period (ie, alirocumab, placebo). Formal statistical testing is not planned. Descriptive statistics will include the same parameters as described for each variable in the double-blind treatment period.

For patients receiving alirocumab in the double-blind treatment period, a combined summary including both the double-blind and open-label treatment period assessments may be considered, referencing the double-blind baseline for variable calculations. Prolonged time between last dose of double-blind treatment and first dose of open-label treatment will need to be taken into consideration when combining longitudinal efficacy data. Again, formal testing is not planned due to the absence of control group.

#### 10.4.3.4. Multiplicity Considerations

In order to handle multiple key secondary endpoints during the double-blind treatment period for the comparison of the alirocumab group and the placebo group, the overall type-I error will be controlled by the use of a hierarchical inferential approach. Statistical significance of the double-blind primary parameter at the 0.05 alpha level is required before drawing inferential conclusions about first key secondary parameter. Inferential conclusions about successive key secondary parameters require statistical significance of the prior one. The hierarchy testing sequence is the order of endpoints as presented in Section 4.2.2.1.

This fixed hierarchical approach will ensure a strong control of the overall type-I error rate at the 0.05 level during the double-blind treatment period.

No further adjustments will be made for other secondary endpoints for which p-values will be provided for descriptive purpose only.

#### 10.4.4. Safety Analysis

No formal inferential testing is planned for safety analyses. Summaries will be descriptive in nature. All safety analyses will be performed on the safety population using the following common rule:

- The baseline value is defined as the last available value before the first dose of the investigational study drug.

##### 10.4.4.1. Adverse Events

All AEs reported in this study will be coded using the currently available version of the MedDRA. The verbatim text, the preferred term (PT), and the system organ class (SOC) will be provided in the patient listings.

##### Definitions

For safety variables, the following observation periods are defined:

- The pretreatment period is defined as the time from signing the ICF to before the first dose of double-blind investigational study drug.
- The double-blind TEAE observation period is defined as the time from first dose of double-blind investigational study drug to the last dose of double-blind investigational study drug + 70 days, or up to the day before first dose of open-label investigational study drug administration, whichever is earlier.
- The open-label TEAE observation period is defined as the time from first open-label study treatment administration to the last open-label study treatment administration + 70 days.
- The post-treatment observation period is defined as the time from the day after the end of the respective TEAE periods up to the patient's end of study.
- Pre-treatment AEs are defined as those that developed, worsened, or became serious during the pre-treatment period.
- Double-blind and open-label TEAEs are defined as those that developed, worsened, or became serious during the respective TEAE periods.
- Double-blind and open-label post-treatment AEs are defined as those that developed, worsened, or became serious during the post-treatment period.

### Analysis

Treatment-emergent and post treatment AEs in both the double-blind and open-label study periods will be summarized in incidence tables by (at least) SOC (sorted by internationally agreed order), and PT (sorted by decreasing frequency, and the number (n) and percentage (%) of patients experiencing an AE). The high level group term and high level term can be added in alphabetical order, as applicable. Multiple occurrences of the same event in the same patient will be counted only once in the tables within the TEAE period. Data conventions for missing or partial AE dates will be addressed in the SAP. The denominator for computation of percentages is the safety set within each treatment group.

Adverse event incidence tables will be provided by treatment group for all types of TEAEs: all TEAEs, all TEAEs of interest (defined with a PT or a pre-specified grouping), TEAE by severity, all treatment-emergent SAEs, and all TEAEs leading to permanent treatment discontinuation.

If any clinically significant signal is detected and further characterization is needed, or for AEs of clinical interest, selected TEAEs will be analyzed using a time-to-event approach (Kaplan Meier methodology) to account for the differential exposure time in all patients. Time from the first dose of the investigational study drug to the first occurrence of the event will be calculated (only the first event will be counted). Patients without any event will be censored at the end of the TEAE period.

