**Open-label Treatment:**

To provide further safety data in this rare patient population, all patients will participate in an open-label treatment period. Regardless of treatment assignment in the double-blind treatment period, patients will receive open-label study drug (alirocumab 150 mg SC Q2W) starting at week 12 (day 85) and continuing through week 24 (end of open-label treatment period, last injection of study drug on day 155/week 22). Patients who are receiving LMT or who are undergoing LDL apheresis should continue a stable dose and regimen and a stable LDL apheresis schedule and settings (as applicable) throughout the duration of the open-label treatment period.

Upon completion of the open-label treatment period, the sponsor may offer each patient the opportunity to participate in an additional lipid-lowering clinical trial. The patient and investigator may decline participation in further treatment trials.

Patients who do not participate in another lipid-lowering study will undergo an 8-week follow-up period. A follow-up phone call will be made at week 32 (corresponding to the 70 day follow-up) to collect AE and concomitant medication information.

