### 8.1.1. Footnotes for the Schedule of Events Table

1. Informed consent/assent will be obtained either at Visit 1a (for patients who need the optional run-in time) or at Visit 1 (for the patients who do not need optional run-in).
2. Injection training will be performed with the patient and/or caregiver during the screening period or at baseline using placebo.
3. After the investigational study drug administration (double-blind and open-label), patients will need to be monitored for 30 minutes.
4. Lipid panel will consist of: total-C, LDL-C, HDL-C, TG, non-HDL-C. Specialty lipid panel will consist of: ApoB, Apo A-1, ratio Apo B/Apo A-1, and Lp(a). Lipid panels should be collected after an approximately 8 hour fast.
5. ECG should be performed before blood samples are collected.
6. On days when a clinic visit coincides with a dosing day, all blood samples (including ADA samples) will be collected immediately prior to LDL apheresis (if applicable) and before the investigational study drug administration, but after study assessments are performed. PK samples will also be used for free and total PCSK9 analysis.
7. Sample should be obtained prior to randomization and will be used to determine HoFH mutation status. Patients on apheresis may collect this during visit 1a.

9. Visit window is  $\pm 3$  days for patients not on apheresis and +1 day for patients on apheresis. Every attempt should be made to ensure all samples are collected immediately prior to LDL apheresis. The timing between the baseline sample collection relative to the most recently completed LDL apheresis procedure should match the timing of the week 12 sample collection relative to the most recently completed LDL apheresis procedure. Depending on the duration between the LDL apheresis procedure and sample collection, the visit window may not apply.

10. This visit is only for patients who do not participate in another lipid-lowering study.

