#### **9.4.6. Follow-up**

Adverse event information will be collected until the patient's last study visit.

Serious adverse event information will be collected until the event is considered recovered, chronic and/or stable, or fatal.

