#### 4.7.1. Adverse Events Variables

The period of safety observation starts from the time when the patient gives informed consent and continues into the following periods:

- The PRE-TREATMENT period: defined as the time from the signed informed consent up to the first double-blind study treatment injection.
- The double-blind treatment-emergent adverse event (TEAE) period: defined as the time from the first double-blind study treatment injection up to the day of the last double-blind study treatment injection + 70 days (10 weeks), or up to the day before first dose of open label investigational study drug administration, whichever is earlier.

The double-blind TEAE period will include:

- The TREATMENT period is defined as the time from the first double-blind study treatment injection up to the day of last double-blind study treatment injection + 21 days, as serum concentration of alirocumab >10 µg/mL is expected for approximately 21 days following administration of 150 mg. Further, in previous studies, alirocumab concentrations declining below this concentration also showed a decrease in effect on LDL-C. For patients entering into the open-label period, the treatment period will be truncated at the day before the first dose of open label investigational study drug administration.
- The RESIDUAL TREATMENT period is defined as the time from the day of last double-blind study treatment injection + 22 days up to the day of last double-blind study treatment injection + 70 days (10 weeks), or up to the day before first dose of open label investigational study drug administration, whichever is earlier.
- The open-label treatment-emergent adverse event (TEAE) period is defined as the time from first open label study treatment injection up to the day of the last open-label study treatment injection + 70 days.

The open-label TEAE period will include:

- The TREATMENT period is defined as the time from the first open-label study treatment injection up to the day of last open-label study treatment injection + 21 days.
- The RESIDUAL TREATMENT period is defined as the time from the day of last open-label study treatment injection + 22 days up to the day of last open-label study treatment injection + 70 days (10 weeks).
- The POST-TREATMENT period: defined as starting the day after the end of the respective TEAE periods up to the patient's end of study.

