- Any lipid assessments within analysis windows up to week 12 will be taken into account (may include few unscheduled lipid data soon after the cut-off date).

- Patients without end of treatment visit (double-blind or open-label) performed at the time of the cut-off date will be considered as ongoing and exposed up to the cut-off date. Therefore:
  - Patients who did not complete the respective treatment period nor prematurely discontinued the study treatment at cut-off date will be analyzed as “ongoing” in the disposition summary.
  - Their TEAE period and treatment period will end at the cut-off date.
  - Their treatment duration will be derived by considering date of cut-off as last injection date.
- Analyses of number of injections, mean injection frequency, percentage of days with under/above-planned dosing and compliance will be performed up to the last injection reported in the e-CRF up to the cut-off date.
- AEs occurring, worsening or becoming serious after the cut-off date will not be included in the analyses. However, any available outcome before database lock, regardless of timing in relation to the cut-off date, of an adverse event starting prior to the cut-off date will be taken into account. Medications, treatment discontinuations/completions and deaths occurring after the cut-off date will not be included in the analyses.
- Post-treatment period, post-study period are not applicable for ongoing patients. Analyses of post-treatment AEs, post-study deaths and post-treatment medications will be performed for patients who either completed or prematurely discontinued the treatment before or at the cut-off date.
- Analysis of status at last study contact and proportion of patients with insufficient follow-up will be provided for patients who either completed or prematurely discontinued the treatment before or at the cut-off date.

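### The open-label TEAE period runs to last dose + 70 days for everyone, but patients who enter another lipid-lowering study have scheduled AE collection for only 14 of those days, so censoring at the end of the period would count unobserved time as event-free

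*Protocol*

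**What the plan says.** **Period.** Protocol 10.4.4.1 (Definitions) sets the open-label TEAE period as "the time from first open-label study treatment administration to the last open-label study treatment administration + 70 days". SAP 4.7.1 agrees: "up to the day of the last open-label study treatment injection + 70 days". Neither gives an earlier end. The double-blind period, defined beside it, does have one: "or up to the day before first dose of open-label investigational study drug administration, whichever is earlier".

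**Collection.** Protocol 9.4.6: "Adverse event information will be collected until the patient's last study visit". Table 1 puts the end-of-open-label visit at Day 169 and the follow-up call at Day 225. Footnote 10, on the call: "This visit is only for patients who do not participate in another lipid-lowering study".

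**Censoring.** Protocol 10.4.4.1 (Analysis) allows a Kaplan-Meier analysis of selected TEAEs if a clinically significant signal needs characterizing, or for events of clinical interest. In that analysis, "Patients without any event will be censored at the end of the TEAE period".

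**Truncation elsewhere.** SAP 7 has a rule for patients still ongoing at the first-step cut-off: "Their TEAE period and treatment period will end at the cut-off date". SAP 6.4 uses the date of last contact, but only to impute a missing last injection date.

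**The concern.** Censoring is valid only up to the point at which an event would have been recorded. A patient who moves to another study at Week 24 leaves this trial's scheduled AE collection on Day 169, yet the definitions keep that patient in the open-label TEAE period until Day 225. If the patient is event-free at Day 169, the censoring rule keeps the patient in the risk set for the rest of the period, when a non-serious event has no scheduled route into the database.

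The definitions also fail to fit these patients in another way. The post-treatment period starts the day after the TEAE period and runs to the patient's end of study. For a rollover patient it would start on Day 226 and end on Day 169.

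At stake is the late part of the open-label safety profile. Safety is a secondary objective, and the protocol gives further safety data as the reason for the open-label period. The amendment history says the window was lengthened from 21 to 70 days to obtain more safety information in a population in which the drug had not been studied. The protocol offers Kaplan-Meier specifically to allow for differing exposure time, and censoring after observation has stopped defeats that purpose. Crude open-label percentages share the problem in milder form, because rollover patients stay in the denominator without being followed for the whole window.

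**Working it through.** **Inputs from the documents**
- First open-label dose Day 85, last Day 155 (Protocol 5.1).
- End-of-open-label visit Day 169, follow-up call Day 225 (Protocol Table 1; SAP 2.3).
- Rollover share r: not stated. Protocol 5.1 says only that the sponsor may offer another trial and that it may be declined.

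**The plan's own figure.** Both documents equate the Week 32 call with the 70-day follow-up: 225 − 155 = 70 days. This reproduces.

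**Observed and unobserved time for an on-schedule rollover patient**
- Observed after last dose: 169 − 155 = 14 days.
- Unobserved: 225 − 169 = 56 days, or 56/70 = 80% of the post-dose window.
- Whole period, counting both end days: 225 − 85 + 1 = 141 days, of which 169 − 85 + 1 = 85 are observed. Unobserved share: 56/141 = 39.7%.
- With the visit and dosing windows, the observed tail is 8 to 20 days off apheresis (166 − 158 to 172 − 152). On apheresis it is 12 to 15 days (168 − 156 to 170 − 155, taking +1 day for the dose and ±1 day for the visit).

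**Effect on a Kaplan-Meier estimate (illustration)**

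Assume a constant hazard h, 10% incidence by Day 169, and no events recorded for rollover patients after Day 169.
- h = −ln(0.9)/85 = 0.00124 per day.
- True incidence at Day 225: 1 − exp(−141h) = 16.0%.
- Under the rule as written, the late hazard is diluted to about (1 − r)h, so the estimate is 1 − 0.9 × exp(−56h(1 − r)), with 56h = 0.0694.

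| Rollover share r | Estimate at Day 225 | Truth |
|---|---|---|
| 0% | 16.0% | 16.0% |
| 25% | 14.6% | 16.0% |
| 50% | 13.1% | 16.0% |
| 80% | 11.2% | 16.0% |
| 90% | 10.6% | 16.0% |

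The exact mixture, 1 − 0.9 × [r + (1 − r)exp(−56h)], gives 14.5% at 25% and 13.0% at 50%, and the same rounded values at the other shares.

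**A second anchor.** Assume instead 10% true incidence over the 140 elapsed days from Day 85 to Day 225, with 84 days observed. The exact mixture then gives 9.0%, 8.1%, 7.1% and 6.1% at shares of 25%, 50%, 75% and 100%.

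**With censoring at last AE collection.** Rollover patients leave the risk set at Day 169, and the tail is estimated from those followed to Day 225. Under the same assumptions this recovers the true value whenever r is below 100%. At 100%, nothing can be estimated beyond Day 169, and the analysis would show that.

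**Does another rule already repair it?** The SAP 7 cut-off rule covers only patients without an end-of-treatment visit at the first-step cut-off, not the final analysis. The SAP 6.4 rule needs a missing injection date. No section says that AEs from a subsequent trial are brought back into this one.

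**The case against.** **The Kaplan-Meier analysis may never be run on open-label data.** This stands. It is conditional, limited to selected events, and not expressly extended to the open-label period. SAP 5.7.1 lists its AE analyses without it. But SAP 1.2.3 lists only one departure from the protocol, and this is not it, so the analysis remains available with its censoring rule attached.

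**A reader might infer that no events at all are collected after Week 24.** The documents do not support that. Under Protocol 9.4.2 a serious event that reaches the investigator is reportable if its onset is within 30 days of end of study. Taking Week 24 as that end, this reaches Day 199, and fatal or drug-related events remain reportable later. This is passive reporting and omits non-serious events, so it narrows the gap without closing it.

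**A reader might extend the point to everyone who leaves early, in either period.** Protocol 7.4.2 keeps patients who stop drug on the original schedule through the follow-up call, and 8.1.2 says those who refuse to continue should be followed for at least 70 days after the last dose. A double-blind patient whose last dose is Day 71 reaches 70 days on Day 141, before Week 24. The 14-day figure belongs to on-schedule completers who roll over; someone who stopped open-label drug earlier but stayed to Week 24 has a longer observed tail.

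**The size is illustrative.** This also stands. The rollover share, the 10% incidence and the constant hazard are all assumptions. SAP 4.7.1 expects concentrations above 10 µg/mL for only about 21 days after a dose, so a falling late hazard is plausible and would shrink the bias.

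**Conclusion.** The rule is wrong as written for one group: patients who complete open-label dosing on schedule and enter another lipid-lowering study. For each such patient who is event-free at Day 169, a Kaplan-Meier analysis of open-label TEAEs would treat 56 days without scheduled AE collection, 40% of the period, as event-free follow-up. Late rates would be understated. Under the first illustration, the shortfall at Day 225 runs from nothing at a zero rollover share to 5.4 percentage points (16.0 − 10.6) at a 90% share.

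It would be too strong to say that the trial's safety comparison is biased. The double-blind TEAE period is cut at the day before the first open-label dose, so the randomized comparison is essentially untouched. The affected summaries are descriptive and uncontrolled, and no inferential safety testing is planned. The case for changing the rule is that it would give a wrong estimate if used, and that correcting it is cheap.

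**What to change.** In Protocol 10.4.4.1 and SAP 4.7.1, end each TEAE period at the earlier of last dose + 70 days and the last date on which AEs were collected for that patient, keeping the existing truncation at the first open-label dose. Censor event-free patients at that date in any time-to-event analysis. With the open-label incidence tables, state how many patients were followed beyond Week 24.

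The cost is one definition line in each document and one count in the tables. No new assessment or data from another trial is needed. The TEAE period becomes shorter for rollover patients, which matches what is collected. Two further steps are not required: a cut at the first dose in the next trial would need a date this study is not shown to collect, and splitting every open-label table at Week 24 is a matter of presentation.
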